8.1.6 Concomitant medications

In general, the use of any concomitant medication/therapies deemed necessary for patient supportive care and safety are permitted. Other anticancer agents, specifically systemic chemotherapy, radiation therapy, or biologic response modifiers are not permitted during the study. Intrathecal chemotherapy is allowed if intended for prophylaxis. No other investigational drug is allowed during the study. Prophylaxis may be used for the prevention of infections or nausea and vomiting. Concomitant medications data will not be collected or entered into the case report form other than hydrea; however, the subject's medication record will contain a list of concomitant medications.

8.2 Lirilumab (BMS-986015)

Lirilumab injection has been developed to be used as an intravenous (IV) infusion for clinical studies. The drug product is a clear to opalescent, colorless liquid, which may contain few particles. It is a sterile, non-pyrogenic, single-use, preservative-free, ready-to-use solution containing 10 mg/mL lirilumab. The 50-mg/Vial and 100-mg/Vial presentations are contained in 6-cc and 10-cc Type I flint glass vials, respectively, closed with 20-mm stoppers, and sealed with aluminum seals. The formulation composition is identical for these two presentations. Each vial of drug product contains the labeled amount of lirilumab drug substance, sucrose, sodium phosphate monobasic, sodium phosphate dibasic, polysorbate 80, and water for

injection. Diluted sodium hydroxide and/or hydrochloric acid solution may be added to adjust the pH to 7.0. A sufficient overfill is included in each vial to account for vial, needle, and syringe holdup. The placebo for lirilumab injection is composed of 0.9% sodium chloride injection (normalsaline; NS).

Drug Product Preparation

Lirilumab injection is administered intravenously either undiluted (10 mg/mL) or diluted in NS to lirilumab concentrations as low as 0.5 mg/mL. The dosing solution is to be infused over 60 minutes through a non-di-2-ethylhexyl phthalate (DEHP) or DEHP IV infusion set with a 0.2-micron polyethersulfone (PES) in-line filter. The drug product is not to be administered as an IV push or bolus injection. Care must be taken to ensure the sterility of the prepared solutions as the drug product does not contain anti-microbial preservatives or bacteriostatic agents. The placebo is administered in a similar fashion.

Recommended Storage and Use Conditions

Lirilumab injection should be stored refrigerated at 2°-8°C and protected from light and freezing. After dilution with NS or transfer from the original vial to an IV bag, the infusion solution must be administered within 4 hours, including the time for infusion, if stored at room temperature, 20°-25°C/ambient light. If not dosed immediately, the infusion solution may be stored in a refrigerator, 2°-8°C, for up to 24 hours, and a maximum of 4 hours, including the time for infusion, of the total 24 hours can be at room temperature, 20°-25°C/ambient light

8.3 Azacitidine

Chemical Name: 4-amino-1-(2-deoxy-β-D-erythro-pentofuranosyl)-1,3,5-triazin-2(1H)-one

Other Names: 4-Amino-1-β-D-ribofuranosyl-1,3,5-triazin-2(1H)-one, 5 AZC, 5-AC, 5- AzaC, 5-azacytidine, 5-AZCR, Antibiotic U 18496, Azacytidine, ladakamycin, Mylosar, NSC-102816, U-18496, WR-183027, Azacitidine

Classification: Antimetabolite, DNA hypomethylating agent

CAS Registry Number: 320-67-2

Molecular Formula: C₈H₁₂N₄O₅ **M.W.:** 244.21

Approximate Solubility: soluble (soluble in caustic soda)

Mode of Action:

Azacitidine is believed to exert its antineoplastic effects by causing hypomethylation of DNA and direct cytotoxicity on abnormal hematopoietic cells in the bone marrow. The concentration of azacitidine required for maximum inhibition of DNA methylation in vitro does not cause major suppression of DNA synthesis. Hypomethylation may restore normal function to genes that are critical for differentiation and proliferation. The cytotoxic effects of azacitidine cause the death of rapidly dividing cells, including cancer cells that are no longer responsive to normal growth control mechanisms. Non-proliferating cells are relatively insensitive to azacitidine.

Pharmacokinetics:

The pharmacokinetics of azacitidine were studied in six MDS patients following a single 75 mg/m² subcutaneous (SC) dose and a single 75 mg/m² intravenous (IV) dose. Azacitidine is rapidly absorbed after SC administration; the peak plasma azacitidine concentration of 750 ± 403 ng/ml occurred in 0.5 hour. The bioavailability of SC azacitidine relative to IV azacitidine is approximately 89%, based on area under the curve. Mean volume of distribution following IV dosing is 76 ± 26 L. Mean apparent SC clearance is 167 ± 49 L/hour and mean half-life

after SC administration is 41 ± 8 minutes.

Published studies indicate that urinary excretion is the primary route of elimination of azacitidine and its metabolites. Following IV administration of radioactive azacitidine to 5 cancer patients, the cumulative urinary excretion was 85% of the radioactive dose. Fecal excretion accounted for <1% of administered radioactivity over three days. Mean excretion of radioactivity in urine following SC administration of ¹⁴C-azacitidine was 50%. The mean elimination half-lives of total radioactivity (azacitidine and its metabolites) were similar after IV and SC administrations, about 4 hours.

Drug-Drug Interactions:

Drug interaction studies with 5-azacitidine have not been conducted. An in vitro study of 5-azacitidine incubation in human liver fractions indicated that azacitidine may be metabolized by the liver. Whether azacitidine metabolism may be affected by known microsomal enzyme inhibitors or inducers has not been studied. The potential of azacitidine to inhibit cytochrome P450 (CYP) enzymes is not known. In vitro studies with human cultured hepatocytes indicate that azacitidine at concentrations of 1.0 μ M to 100 μ M does not induce CYP 1A2, 2C19, or 3A4/5. Hydroxyurea is known to inhibit ribonuclease reductase, a key enzyme required for the incorporation of 5-azacytidine residues into DNA. Therefore, hydroxyurea may potentially limit the clinical activity of 5-azacytidine and its use during this clinical trial should be avoided.

Route of Administration: Intravenous

Preparation: Azacitidine is a cytotoxic drug and, as with other potentially toxic compounds, caution should be exercised when handling and preparing suspensions. If reconstituted azacitidine comes into contact with the skin, immediately and

thoroughly wash with soap and water. If it comes into contact with mucous membranes, flush thoroughly with water.

How Supplied: Azacitidine is supplied as 100 mg vials of lyophilized powder.

Storage: Store un-reconstituted vials at 25° C (77° F); excursions permitted to 15°-30° C (59°-86° F) (See USP Controlled Room Temperature). There is no need to protect azacitidine from exposure to light.

Handling and Disposal: Procedures for proper handling and disposal of anticancer drugs should be applied.

Reported Adverse Events and Potential Risks:

In clinical studies, the most commonly occurring adverse reactions were nausea (70.5%), anemia (69.5%), thrombocytopenia (65.5%), vomiting (54.1%), pyrexia (51.8%), leucopenia (48.2%), diarrhea (36.4%), fatigue (35.9%), injection site erythema (35.0%), constipation (33.6%), neutropenia (32.3%), and ecchymosis (30.5%). Other adverse reactions included dizziness (18.6%), chest pain (16.4%), febrile neutropenia (16.4%), myalgia (15.9%), injection site reaction (13.6%), aggravated fatigue (12.7%) and malaise (10.9%).

Because treatment with Azacitidine is associated with neutropenia and thrombocytopenia, complete blood counts should be performed as needed to monitor response and toxicity, but at a minimum, prior to each dosing cycle.

Because azacitidine is potentially hepatotoxic in patients with pre-existing hepatic impairment, caution is needed in patients with liver disease. In addition, azacitidine and its metabolites are substantially excreted by the kidneys and the risk of toxic reactions to this drug may be greater in patients with impaired renal function.

Because elderly patients are more likely to have decreased renal function, it may be useful to monitor renal function.

Azacitidine may cause fetal harm. While receiving treatment with Azacitidine, women of childbearing potential should avoid becoming pregnant, and men should avoid fathering a child. In addition, women treated with Azacitidine should not nurse.

Reconstitution Recommendations for Azacitidine for IV Administration

General Cautions:

Azacitidine's active agent, azacitidine, is hydrolytically unstable. Administration of reconstituted drug product must be completed within one hour of reconstitution. Azacitidine is incompatible with 5% Dextrose solutions, Hespan, or solutions containing Bicarbonate. At no time should diluents with a pH below 6.0 be used.

Procedure:

1. Reconstitute each Azacitidine drug product vial with 10mL of Sterile Water for Injection, USP (SWFI).
2. Shake/roll the vial until all solids are dissolved as determined by visual inspection. Vigorous shaking is allowed if required to ensure complete dissolution. The reconstituted solution should be clear.
3. The concentration of the reconstituted drug product is 10 mg/mL Azacitidine.
4. Withdraw and dilute the required amount of reconstituted drug product in an appropriate container with either 0.9% Sodium Chloride Injection, USP, or Lactated Ringer's Injection, USP. The final volume of the diluted drug product should be no greater than 100mL.
5. If a patient requires more than one vial of Azacitidine, reconstitute each vial as described above and dilute all required, reconstituted Azacitidine into a single container with a total volume not to exceed 100mL. (Final concentration should be <10 mg/mL).

6. The reconstituted and diluted Azacitidine should be administered intravenously over a 10 - 40 minute period. **The administration must be completed within one hour of the reconstitution time.**
7. Follow the administration with a 10 mL normal saline flush.

8.4 Study Drug Destruction

All expired or unused study drugs will be destroyed or returned as per institutional and investigational pharmacy standard operating procedures, with supplier agreement.

9.0 Patient Evaluation

Pre-Treatment Evaluation: All pretreatment studies should be obtained within 14 days (± 3 days) of entry into the trial, unless otherwise stated.

1. A complete history and physical, including assessment of baseline adverse events.
2. CBC, platelet count, differential (differential can be omitted if WBC is $\leq 0.5 \times 10^9/L$).
3. Creatinine, total bilirubin, ALT, AST, amylase, lipase, and TSH.
4. Pregnancy test (urine or plasma) in females of childbearing potential should be required within 24 hrs of study enrollment or randomization, then every 6 weeks. After discontinuation from nivolumab these should be repeated at approximately 30 days and approximately 70 days [or more frequently if required by local standard].
5. Bone marrow aspirate during the last 14 days preceding study initiation. Cytogenetics will be obtained prior to therapy in patients known to have cytogenetic abnormalities at the time of diagnosis or relapse (results from prior analysis within 4 weeks can be used for this purpose).
6. Chest x-ray.
7. Pretreatment optional correlative studies. Every effort will be made to collect all samples at all time points for all patients; however, missing collection in

one or more of these time points in occasional patients will not be considered a protocol deviation/violation.

10.0 Evaluation during Treatment

All evaluations can vary +/- 3 days.

Complete history and physical and assessments for toxicity should be performed weekly for the first course, then once per course.

CBC, platelet count, differential, creatinine, albumin, SGPT, electrolytes, total bilirubin, and TSH weekly for the first course, then once per course at the discretion of the treating physician.

Bone marrow aspiration with cytogenetics (if abnormal at baseline) on Day 28 of Course 1 (+/- 3 days) and afterwards every 3 months or as indicated to document response or to decide on therapy administration. Once a response is obtained, bone marrow sampling can be repeated at the discretion of the treating physician to confirm remission status or document loss of response.

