11.0 Criteria for Response

For MDS, the International Working Group criteria will be use to assess response (11).

Remission is calculated from date of first response until relapse. Survival is calculated from start of therapy until death from any cause.

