14.0 Correlative Studies

Correlative studies will be considered exploratory and will be performed whenever possible. Bone marrow and blood samples will only be collected on patients who consent to protocols: LAB01-473 and PA13-0291. If a patient's baseline correlative bone marrow sample is not collected for any reason, no additional correlative bone marrow or blood samples will be collected on the patient. Additionally, any samples that

are missed are not considered a protocol deviation.

Gene sequencing. Patients not consented through the Apollo program (PI [name]) will be offered consenting under protocol LAB03-473 at baseline and their genomes will be sequenced using that platform. 5 cc of blood in a green tube will be required for this analysis. If the patient participates on LAB01-473, the following samples will be collected at the specified time points:

- Bone Marrow aspirate: will be baseline, C1D28, thereafter every 3 cycles, at time of best morphological response and at progression.
- Peripheral Blood: screening, prior to each dose of study drug during the first 3 cycles, at time of best morphological response, and at progression.

Immune assessment. Tumor tissue, blood samples and bone marrow aspirate will be collected on a separate IRB approved laboratory protocol (PA13-0291) for immune monitoring as previously published,¹⁸⁻²¹ under the supervision of the Immunotherapy Platform. In tumor tissues, immunohistochemical studies will be performed to evaluate tumor and immunological cell markers such as CD4 and CD8 T cells. In peripheral blood, we will also evaluate tumor and immune cell populations including but not limited to CD4 and CD8 T cells in pre and post therapy samples.

Peripheral blood. Up to 150 mL (within 24 hours) of peripheral blood will be collected under an IRB-approved laboratory protocol (PA13-0291) for testing of biomarkers described in this clinical protocol at the following time points, if the patient agrees to participate on PA13-0291:

- At screening
- Prior to each dose of study drug during the first 3 cycles. On days when both Nivolumab and Liriumab are administered, a blood sample will only be collected prior to the Nivolumab dose.
- At time of best morphological response
- At progression

The treating physician or designee will have the option to cancel the laboratory protocol collection for patient safety without protocol deviation.

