All patients who received any dose of the study agent will be included in the analysis for efficacy and safety. Demographic/clinical characteristics (i.e. including duration of response) and safety data of the patients will be summarized using descriptive statistics such as mean, standard deviation, median and range. For the primary efficacy analysis, we will estimate the ORR for the experimental treatments, along with the 95% credible intervals. The association between ORR and patient's clinical characteristics will be examined by Wilcoxon's rank sum test or Fisher's exact test, as appropriate. Toxicity type, severity and attribution will be summarized for each patient using frequency tables. The distribution of time-to-event endpoints (PFS and OS) including overall survival and event free survival will be estimated using the method of Kaplan and Meier. Comparisons of time-to-event endpoints by important subgroups will be made using the log-rank tests. Paired t-tests will be used to determine the immunological and molecular changes in the peripheral blood and bone marrow from baseline to the time of response, and to the time of disease progression.

16. Confidentiality Plan

Confidentiality will be maintained via codification of data collected and restriction of access to the data. In particular, to be authorized to use the PDMS database, M. D.

Anderson employees must have an institutional USERID assigned through the Information Services Security Department. State regulations for database computer access are followed. ALL database analysts regularly log and monitor the system access and log-in activity. All unsuccessful attempts to access the ALL database are logged to a file that is reviewed daily by the ALL database coordinator. If the user has updated patient data, they will be prompted for the password upon exiting the ALL database. If the password is not verified, an automated e-mail is sent to the ALL database coordinator, and a log is created. Users are required to change their password every three months. The passwords are stored in an encrypted format.

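### Marrow sampling becomes discretionary once a patient responds, so relapse can be dated late and remission duration and PFS overstated; the SAP has no analysis that allows for this

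*Combined protocol and SAP*

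**What the plan says.** Section 10.0 (Evaluation during Treatment) sets a marrow on Day 28 of Course 1 and "afterwards every 3 months or as indicated to document response or to decide on therapy administration". It then changes the rule for responders: "Once a response is obtained, bone marrow sampling can be repeated at the discretion of the treating physician". The stated purpose of these later marrows is "to confirm remission status or document loss of response", so they serve to detect the event that ends remission.

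Other monitoring in the same section does not depend on response. The clinical visit is fixed: "Complete history and physical and assessments for toxicity should be performed weekly for the first course, then once per course". Blood counts are less firm: "then once per course at the discretion of the treating physician".

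Section 14.0 (Correlative Studies) plans research marrows regardless of response: "Bone Marrow aspirate: will be baseline, C1D28, thereafter every 3 cycles", and also at best response and at progression. They are drawn only in patients who consent to separate laboratory protocols. They stop if the baseline correlative marrow was not collected, and a missed sample is not a deviation.

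Section 11.0 defines the duration: "Remission is calculated from date of first response until relapse". The analysis plan in Section 15.0 says "The distribution of time-to-event endpoints (PFS and OS") will be estimated by Kaplan-Meier, with log-rank comparisons of important subgroups. Duration of response is summarised by mean, standard deviation, median and range. No rule is given for what counts as progression, for censoring, or for events found after a long gap between assessments.

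**The concern.** Remission duration and PFS end on the date when someone finds the relapse. In the main study the default marrow interval ends at response and continues for everyone else, so the interval depends on the outcome. If responders are looked at less often, a relapse that only a marrow would show is found later, and the measured remission lengthens with no change in the disease.

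The shift would fall on the patients who make a regimen look active, and a cohort with more responders would have more patients on the looser schedule. PFS is a named secondary outcome in Section 1.0. Because the mean duration of response is a planned summary, a longer average detection delay would enter a reported figure directly.

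**Working it through.** **Plan's own figure.** The documents give no median, event count or precision for remission duration or PFS, so there is nothing to reproduce.

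**Inputs from the documents.** Marrow every 3 months before response and no set interval afterwards (Section 10.0). Counts once per 28-day course, that is 28/30.44 = 0.92 months (Sections 10.0 and 15.0). Correlative marrows every 3 cycles, that is 84 days or about 2.8 months (Section 14.0).

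**Assumptions.** True remission is exponential with median m of 6 to 18 months. The post-response marrow interval τ is 3, 6 or 12 months. A share s of relapses is visible on 4-weekly counts. None of these values is in the documents.

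**Step 1: relapse visible only on marrow (s = 0).** With λ = ln 2 / m and relapse dated at the next marrow:

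mean dated duration = τ / (1 − e^(−λτ)); mean delay = mean dated duration − 1/λ.

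For m = 6, 1/λ = 8.66. At τ = 3 the dated mean is 3/(1 − 0.7071) = 10.24, at τ = 6 it is 6/(1 − 0.5) = 12.00, and at τ = 12 it is 12/(1 − 0.25) = 16.00. For m = 18 the three values are 27.50, 29.08 and 32.43, with 1/λ = 25.97.

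| Median m | Delay, τ = 3 | Delay, τ = 6 | Delay, τ = 12 | Excess, 6 vs 3 | Excess, 12 vs 3 |
|---|---|---|---|---|---|
| 6 | 1.59 | 3.34 | 7.34 | 1.76 | 5.76 |
| 9 | 1.56 | 3.23 | 6.91 | 1.67 | 5.35 |
| 12 | 1.54 | 3.17 | 6.69 | 1.63 | 5.14 |
| 18 | 1.53 | 3.12 | 6.46 | 1.59 | 4.93 |

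All figures are in months. Some delay exists even at 3 months; the concern is the excess over that.

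**Step 2: some relapses visible on counts.** The excess is close to (1 − s) times the marrow-only value. For s = 0.5 and τ = 6 this gives 0.5 × 1.59 = 0.80 to 0.5 × 1.76 = 0.88. Simulation over the four medians gave:

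| Share s seen on counts | Excess, 6 vs 3 months | Excess, 12 vs 3 months |
|---|---|---|
| 0 | 1.6 to 1.8 | 4.9 to 5.8 |
| 0.5 | 0.8 to 0.9 | 2.5 to 2.9 |
| 0.8 | 0.3 to 0.4 | 1.0 to 1.2 |
| 1.0 | about 0 | about 0 |

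If physicians keep responders on 3-monthly marrows, the excess is 0 whatever s is.

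**Step 3: would an interval-censored analysis help?** Take m = 8, τ = 6 and marrow-only relapse. The mean dated duration is 6/(1 − 0.5946) = 14.80, so an exponential model fitted to detection dates tends to a median of 0.6931 × 14.80 = 10.3 months against a true 8. In simulation with 14 responders (0.70 × 20), dating at detection gave 10.1 months. Treating relapse as lying between the last negative and first positive marrow gave 7.8.

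**Step 4: precision.** With 14 relapses, even exactly dated, a 95% interval for an exponential median multiplies and divides it by about exp(1.96/√14) = 1.69, so 8 months would carry roughly 4.7 to 13.5.

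**Step 5: what does not move.** The futility limits (1, 4, 7 responders at 5, 10, 15 patients), the toxicity limits (4, 7, 9) and the stopping probabilities checked in Tables 3 and 6 (for example 0.1241 at 30% toxicity and 70% ORR) reproduce from the stated priors. They use response and toxicity counts only. ORR is assessed after 6 cycles, and survival runs to death from any cause.

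**The case against.** The strongest reply is that the text permits sparser sampling and does not require it. The physician may repeat the marrow precisely to document loss of response, and the schedule for patients without a response also carries an as-indicated qualifier. This stands. A reader might infer that relapse is looked for less often and that remission and PFS are overstated; the documents show only that this can happen.

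Second, relapse need not wait for a marrow. Response includes hematological improvement, and visits and counts are planned each course. This also stands, and it is why the estimate runs down to zero. It does not close the gap, because the counts carry their own discretionary wording.

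Third, a reader might see a contradiction between Sections 10.0 and 14.0. There is none: an optional research marrow is compatible with a discretionary clinical one. Where drawn, it keeps a similar interval and reduces the problem, but it depends on separate consent and cannot be relied on.

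Fourth, a reader might expect a biased test of PFS in responders against non-responders. Section 15.0 speaks only of important subgroups and names no such comparison.

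Finally, these are exploratory or descriptive endpoints in cohorts of 20, and no go/no-go rule uses them. That limits the consequence but leaves the outcome-dependent schedule in place.

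**Conclusion.** The concern holds as a possibility built into the schedule. After response no main-study marrow is mandatory, and the planned analysis takes no account of when patients were assessed. If responders move from 3- to 6-monthly marrows, mean remission duration rises by about 1.6 to 1.8 months when all relapses are marrow-only, 0.8 to 0.9 when half show on counts, and about 0 when all do. At 12-monthly marrows the marrow-only excess would be about 4.9 to 5.8 months. These figures rest on exponential remission with assumed medians of 6 to 18 months, an assumed interval and an assumed count-visible share.

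The direction for responders' PFS is the same, but its size cannot be established because the plan does not define the PFS event or its censoring. The conclusion does not extend to ORR, OS or the stopping rules.

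**What to change.** In the Statistical Analysis Plan part of Section 15.0, keep Kaplan-Meier and add a sensitivity analysis of remission duration and PFS that treats relapse or progression as interval-censored between the last negative and first positive assessment. Use the per-course counts and every marrow drawn, including the correlative marrows in Section 14.0.

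State which assessment counts as negative. For relapse found on marrow, the lower bound should be the last clear marrow; a normal count taken as negative would bring the late dating back in. For loss of response shown by counts, the last clear count serves.

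Report the actual intervals between marrows and between counts by response status, so that readers can see whether sampling thinned out.

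Do not add mandatory marrows, and do not restrict when the physician may take one.

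The cost is one extra analysis, plus the date and result of each assessment in the analysis data. Its intervals will be wide at 20 patients per cohort, and it is only approximate where a marrow was triggered by suspected relapse, because the assessment time then depends on the event.
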